If patients meet all inclusions and exclusion criteria, we will check with their nephrology providers prior to approaching participants to ensure their candidacy in our study.

Baseline Visit

During the baseline visit, participant eligibility is confirmed, written consent is obtained, and demographic, co-morbidity, and laboratory data are collected. A brief physical examination is performed and three automated office BP readings in the seated position followed by two standing BP readings are recorded one minute apart after five minutes of quiet rest. At the baseline visit, enrollees are provided with a QardioArm® device and trained to use the device to take standardized home BP measurements.

Participants are asked to take home BPs for a one-week baseline period to ensure continued eligibility and compliance with our protocol prior to randomization, with a minimum of 6 readings required over the one-week period. Participants are also asked to complete 24-hour ambulatory blood pressure monitoring (ABPM) during their baseline period. Patients who refuse to undergo 24-hour ABPM are not excluded from study.

Randomization

Eligible patients who complete the one week of baseline home readings will be randomized to either a home SBP target of <120 mmHg (intervention group) or 130-140 mmHg (usual care group) in 2:1 ratio until 75 participants are enrolled, and participants will be subsequently randomized in 1:1 ratio thereafter. The rationale for the 2:1 ratio for the first 75 patients is to ensure that we initially capture enough safety data on participants randomized to intervention, but we plan to transition to 1:1 ratio randomization thereafter. We will conduct a sensitivity analysis comparing the effect during the 2:1 randomization phase of the trial and 1:1 phase to determine if there is an interaction between the intervention and the phase of the trial.

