PERFORMANCE Trial

NCT02975505

Document date: 2/13/2025

Statistical Analysis

Safety outcomes, or rates of adverse events, will be tallied using simple proportions and descriptive statistics. Intention-to-treat analysis will be performed. Stratified analyses by diabetes status will be performed given the lack of robust trial data to support intensive BP lowering in patients with diabetes. We will also test for differences in the composite rates of hospitalizations, emergency room visits, and hyperkalemia in the two arms. We will explore differences in the rates of ESKD or cardiovascular events and determine if there is any effect modification of the intervention by level of proteinuria or by diabetes. For patients lost to followup, we plan to use chained multiple imputation to perform analyses.

Sample Size Rationale

We estimate that randomly assigning 90 participants to intensive versus less intensive SBP control would provide 80% power (with 2-sided α of 0.05) to detect a 6-mmHg difference in SBP (with SD of the change in SBP within each arm to be 10 mmHg) between the two arms at month 12. Anticipating approximately a 20% dropout rate given the pill burden and 10% loss to follow-up rate given the traditional known challenges in recruiting and retaining patients with advanced CKD to an interventional trial, we planned to enroll up to 120 participants

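### The SAP's 80% power for 90 patients does not follow from its own attrition, allocation and intention-to-treat statements; depending on what dropout means, power is about 76–77%, or anywhere from 67% to 86%

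*SAP*

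**What the plan says.** SAP, Sample Size Rationale: "We estimate that randomly assigning 90 participants to intensive versus less intensive SBP control would provide 80% power", at two-sided alpha 0.05, "to detect a 6-mmHg difference in SBP", "with SD of the change in SBP within each arm to be 10 mmHg". The time point is month 12. Attrition is given in two parts, "Anticipating approximately a 20% dropout rate given the pill burden and 10% loss to follow-up rate", and the answer to both is to enrol up to 120.

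SAP, Statistical Analysis: "Intention-to-treat analysis will be performed". Chained multiple imputation is planned for patients lost to follow-up. No model for the SBP comparison is described.

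Protocol, Randomization: patients are allocated "in 2:1 ratio until 75 participants are enrolled, and participants will be subsequently randomized in 1:1 ratio thereafter".

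Protocol, Sample size rationale: 96 patients, month 8, about 25% dropout and 120 enrolled, with the same 6 mmHg, SD of 10 and 80% power.

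Protocol, Outcomes measures: the primary outcome is the feasibility of a separation of at least 6 mmHg between the arms at month 8.

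**The concern.** The SAP names two kinds of attrition with different causes and treats both as a reason to enrol more patients. That suits patients whose outcome is missing. It does not suit patients who stop the strategy because of pill burden but are still measured. Under intention to treat they stay in their arm, and the arm difference shrinks by whatever effect they lose. Extra patients can offset this, but only if the calculation uses the smaller difference, and the SAP keeps the full 6 mmHg.

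The inflation also looks short on its simplest reading, since 120 yields 90 only if total loss is 25%. The allocation behind the 90 is not stated, and the protocol's allocation is unequal.

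The 6 mmHg separation is the trial's primary question. If 6 mmHg is the effect in patients who stay on strategy, forecast dropout alone could bring the expected separation below the trial's own threshold. A negative result judged against a nominal 80% could then be taken as infeasibility of strict control.

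**Working it through.** **Inputs.** From the SAP: difference δ = 6 mmHg, SD σ = 10 mmHg, two-sided alpha 0.05, N = 90, 120 enrolled, 20% dropout, 10% loss. From the protocol: the allocation rule. Not in either document: the effect retained by patients who drop out. This is an assumption, ranged from 0 to 100%.

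**Method.** Two-sample t test with noncentrality λ = δ / [σ √(1/n₁ + 1/n₂)] and n₁ + n₂ − 2 degrees of freedom.

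**1. The SAP's figure.** With 45:45, λ = 6 / (10 √(2/45)) = 2.85 and power is 80.4%. The 90 reproduces as an equal-allocation number.

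**2. Expected allocation.** Intervention: 75 × 2/3 + 45/2 = 72.5. Usual care: 75 × 1/3 + 45/2 = 47.5. Splitting 90 in that ratio gives 54.4:35.6, λ = 2.78 and power 78.6%. Allocation alone costs 1.8 points, and 94 patients would be needed for 80%.

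**3. Both losses remove outcome data.**
- Remaining from 120: 120 × (1 − 0.30) = 84 if the rates add, or 120 × 0.8 × 0.9 = 86.4 if they multiply.
- Power at the expected split and 6 mmHg: 75.7% (84) and 76.9% (86.4).
- Enrolment needed to keep 90: 90/(0.8 × 0.9) = 125, or 90/0.70 = 129.
- The 120 matches 90/0.75, that is, 25% total loss.

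**4. Dropouts stay in the analysis and only the 10% are lost.** Analysed: 120 × 0.9 = 108, split 65.25:42.75. If 20% of the intervention arm is off strategy and keeps a fraction r of the effect, and usual-care SBP is unaffected by dropout, the expected difference is 6 × (0.8 + 0.2r).

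| Effect retained (r) | Expected difference | Power |
|---|---|---|
| 0% | 4.8 mmHg | 67.6% |
| 25% | 5.1 mmHg | 72.9% |
| 50% | 5.4 mmHg | 77.6% |
| 75% | 5.7 mmHg | 81.9% |
| 100%, or 6 mmHg already the intention-to-treat difference | 6.0 mmHg | 85.6% |

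The table keeps the SD at 10. At r = 0, mixing patients on and off strategy raises the intervention-arm variance to 100 + 0.2 × 0.8 × 36 = 105.76, and power is 66.6%; hence about 67%. Power passes 80% at roughly r = 65% (5.58 mmHg).

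**5. Sensitivity to the 10% loss.** If all 120 are measured and r = 0, power is 71–72%, depending on whether the extra variance is included.

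**The case against.** A reader might infer that the power as written is about 67%. The documents do not support that as a settled figure. It needs dropouts who are still measured, who all revert fully to usual-care SBP, and a further 10% lost. The SAP states neither of the first two conditions. It is the lower end of a range.

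The strongest opposing case is that 6 mmHg is already the intention-to-treat difference. Both documents describe it as a difference between arms, not as one among patients who stay on strategy. The home SBP targets (below 120 versus 130–140 mmHg) are at least 10 mmHg apart, so 6 could already allow for incomplete attainment. Multiplying by 0.8 would then count non-adherence twice, and power with 108 analysed is 86%, better than printed. This reading is open, but the SAP does not state it. If it is meant, the 20% should not also be taken off N.

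Dropout may also mean leaving the study. The protocol allows disenrolment and uses dropout purely to inflate enrolment. That reading gives 76–77%, a shortfall of a few points. If the two rates overlapped so that 25% were lost in total, 90 would remain and power would be 78.6%, close to 80%. The SAP lists them as separate rates with separate causes and mentions no overlap.

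Two further points stand. Allocation is a minor contributor, and the equal split behind the 90 is inferred. The intention-to-treat sentence follows one about safety, so applying it to SBP is a reasonable reading rather than an explicit instruction; no other analysis set is given.

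**Conclusion.** The point holds as a failure of the SAP's power statement to follow from its own inputs. The arithmetic for 90 is sound at equal allocation. What fails is the step from 120 enrolled, with 20% and 10% attrition, to 90 patients with the full 6 mmHg.

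- If both losses remove data, power is about 76–77%.
- If dropouts stay and only 10% are lost, it runs from about 67% to 86%, according to the effect they retain or whether 6 mmHg is already diluted.

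In the second case 80% could be reached at about 65% retained effect, but the SAP makes no such assumption. The figures rest on SD 10, the expected rather than realised allocation, full enrolment of 120, and imputation that adds no information beyond the observed outcomes. The documents do not show that the trial is underpowered. They show that the printed 80% is unsupported and that a key term is undefined. Correcting it matters because the 6 mmHg separation is the primary question, but it does not call for a change in design.

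**What to change.** Keep 120 patients and rewrite the SAP's Sample Size Rationale so that it:

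1. gives the expected allocation of 72.5:47.5;
2. defines dropout and says whether those patients remain measured and analysed;
3. says whether 6 mmHg is the on-strategy or the intention-to-treat difference;
4. gives the matching power.

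If dropouts leave without outcome data, the statement would be 84 to 86 analysed and about 76–77%. If they stay and 6 mmHg is the on-strategy effect, it would be 108 analysed and 67–86%, with the retained-effect assumption shown. If 6 mmHg is the intention-to-treat difference, it would be about 86%, with the 20% no longer deducted from N.

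Before one statement is used in both documents, reconcile the SAP (90 patients, month 12, 20% plus 10%) with the protocol (96 patients, month 8, 25%). The SAP should also say explicitly that intention to treat applies to the SBP comparison.

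The cost is wording only, with no added patients or visits. The downside is a possibly less favourable stated power.
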